#### Table footnotes:

- a Full medical history at screening, review/update of history only at subsequent visits.
- b Ophthalmological examinations will be performed by an ophthalmologist at screening, at study termination and if clinically indicated.
- c ONLY if the screening serum pregnancy test was performed more than 1 day previously.
- d After screening and baseline, urine pregnancy test which if positive, confirm with serum test.
- Study drug to be taken twice daily, first dose in clinic on days when PK sampling occurs i.e., Cycle 1 on Visit 2 (Day 1) and Visit 5 (Day 22), remaining doses on all other days to be self-administered by patient.
- f PK blood samples will be collected prior to first morning dose and at 0.5 hours, 1 hour, 2 hours, 4 hours, 6 hours, 8 hours and 12 ±2 hours post-dose. Pharmacodynamic and peripheral blood mononuclear cells (PBMC) blood samples will be collected prior to first morning dose and at 4 hours post-dose.
- Pharmacodynamic, PK and PBMC blood samples are required at baseline where feasible. Additional biomarkers and DNA sequence analysis may be identified and measured as appropriate by collection of whole blood prior to dosing initiation and after drug levels have reached steady-state. Steady state refers to patients who have received at least 5 days, or 10 consecutive doses, of investigational product. If patients are not at steady state, these assessments will be rescheduled and completed at the next visit in which steady state is achieved. Leukemic cell genotyping by DNA analysis may be performed to identify somatic alterations, relying on either available stored samples or freshly collected samples.
- h Bone marrow aspirate and/or biopsy. Peripheral, Geimsa and Iron stained slides to be provided with each bone marrow aspirate or biopsy. Bone marrow aspirate and/or biopsy slides will not be shipped to a third party. As such, the site may utilize BM aspirates performed in clinical practice as SOC, as long as they are collected within the screening window (-28 days). Bone marrow cytogenetics (cytogenetics should include at least 20 clones). Bone marrow aspirates may be used to evaluate biomarkers of drug response.
- i Chemistry (to include calcium and inorganic phosphorus), hematology and urinalysis. After Cycle 2, clinical chemistry (to include calcium and inorganic phosphorus), hematology and urinalysis may be performed once per cycle or more frequently at the investigator's discretion.
- j Patients with a normal ECG in Cycle 1 need not have repeat ECGs in subsequent cycles. Patients should be supine for 5 minutes prior to the ECG.
- k Bone marrow aspirates will be obtained at Screening, Cycle 1-Day 22, and every other cycle thereafter. At treatment discontinuation visit, bone marrow aspirates will not be obtained if termination is due to disease progression.

\* Physical examinations should be symptom driven after the Screening Visit.

\*\* Assessments of current disease status will be obtained at Screening, Cycle 1–Day 22, and every other cycle thereafter.

## Table 3.2 Pharmacokinetic Parameters to be Estimated after Dose 1 and at Steady State

$C_{max}$	Peak plasma concentration determined manually by visual inspection of plasma concentration vs. time figures on the untransformed (linear) scale of measurement
t max	Time to reach the peak plasma concentration determined manually by visual inspection of plasma concentration vs. time figures on the untransformed (linear) scale of measurement
AUC 0-12	Area under the plasma concentration time curve from 0 to 12 hours post-dosing, calculated by linear/log trapezoidal method
AUC 0-last	Area under the plasma concentration-time curve from time 0 to time of last observation after dosing calculated by linear/log trapezoidal method
$\lambda_Z$	Elimination rate constant, determined by linear regression of at least 3 points on the terminal phase of the log-linear plasma concentration-time curve. The correlation coefficient ( $r^2$ ) for the goodness of the fit of the regression line through the data points has to be 0.85 or higher, for the value to be considered reliable. If the WinNonlin data points are not on the linear portion of the terminal slope, the data points will be selected manually prior to calculation of $\lambda_Z$
t 1/2	Terminal half-life, defined as 0.693 [ln(2)] divided by $\lambda_Z$

Table 3.3 Study Medication Dosing and Pharmacokinetics/Pharmacodynamics Chart

		Study Days					
	1	8 ± 1	15 ± 1	22 ± 1			
BVD-523 dosing [a]	X	X	X	X			
Pharmacokinetics	X			X			
Pharmacodynamics	X			X			

a Dosing is twice daily in 21-day cycles until disease progression. Patients will take their study medication in the clinic on PK days. Patients may be treated beyond disease progression for additional 21-day cycles at the same or escalated dose level at the Investigator's discretion. Study medication for a week of dosing should be dispensed at each visit for treatment Cycles 1 and 2. For treatment cycles after Cycle 2, study medication will be dispensed to support the entire 3 week cycle.

### 4 SAMPLE SIZE CONSIDERATIONS

The expected sample size is 60 subjects: 20 in Part 1 and 40 in Part 2 (20 subjects each in RAS mutant positive and RAS mutant negative groups). This sample size was selected based on the sample size for similar Phase 1 oncology clinical trials.

### 5 ANALYSIS POPULATIONS

The following population definitions will be used in study summaries and analyses.

#### 5.1 SCREENED

The Screened Population will consist of all patients who have signed the informed consent. The screened population will be used for disposition tables.

### 5.2 SAFETY

The Safety Population will consist of all subjects receiving at least 1 dose of study drug. Demographic and baseline characteristics will be tabulated for the Safety population. The Safety population will be used for all safety analyses. Safety analyses from Part 1 will be presented overall as well as broken down by dose level. Safety analyses from Part 2 will be presented overall as well as broken down by dose level, specifically at the RP2D dose of 600 mg.

#### 5.3 MODIFIED INTENT-TO-TREAT

The modified Intent-to-Treat (mITT) Population will consist of all subjects who have a screening visit / sign the informed consent and had no screening failures/were eligible for treatment regardless of whether or not they have received treatment. Demographic and baseline characteristics will be tabulated for the mITT population. Additionally, the mITT population will be used for calculating response in Part 2.

### 5.4 PER PROTOCOL

The Per Protocol (PP) Population will consist of all subjects in the mITT population who receive at least 1 dose of study drug, complete the first protocol-specified tumor measurement evaluation (except for study drug-related AE), and complete the study without a major protocol deviation (see Section 8.6). Demographic and baseline characteristics will be tabulated for the PP population. Additionally, the PP population will be used for calculating MTDs in Part 1 and response in Part 2.

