6.	Any cancer-directed therapy (chen etc.) within 28 days or 5 half-lives	notherapy, radiotherapy, hormonal, (whichever is shorter).	therapy, biologic or immunotherapy,		
7. 1 1	Any concurrent or prior use of an i lives (whichever is shorter) prior to termination of the investigational of related toxicity except alopecia sho	nvestigational drug (including ME o the first dose of BVD-523. A mi drug and administration of BVD-52 ould have recovered to Grade 1 or	X inhibitors) within 28 days or 5 half- nimum of 10 days between 23 is required. In addition, any drug- less.		
8. ] 1	Received chemotherapy regimens nitrosourea or mitomycin C). Rece with limited potential for delayed t	with delayed toxicity within the lase eived chemotherapy regimens give toxicity within the last two weeks.	st four weeks (six weeks for prior en continuously or on a weekly basis		
9.	Ongoing anticoagulant therapy tha who require anticoagulant therapy should not be considered for this st	t cannot be held if necessary to per and cannot be maintained on low r tudy.	rmit bone marrow sampling. Patients molecular weight heparin (LMWH)		
10.1	Major surgery within 4 weeks prio	r to first dose.			
11.1	Pregnant or breast-feeding women				
12.	Any evidence of serious active infe enrollment and on active treatment	ections (subjects who have been fe t would not be considered excluded	ver-free for 24 hours prior to 1).		
13. i	Any important medical illness or a in this study (based on the investig	bnormal laboratory finding that we ator's judgment).	ould increase the risk of participating		
14.	A history or current evidence/risk	of retinal vein occlusion (RVO) or	central serous retinopathy (CSR).		
15.	Concurrent therapy with drugs knows strong inducers of CYP3A4 (for list	own to be strong inhibitors of CYP st of non-permitted drugs, see App	1A2, CYP2D6, and CYP3A4, or endix 1).		
Test	Product, Dose and Mode of Adn	ninistration:			
Part 21 da subje reduc (whie	Part 1: BVD-523, starting at an oral dose of 300 mg taken with at least 8 ounces of water twice-daily for each 21 day cycle, with escalating dose levels (classic 3+3 design). Dosing of each subject will continue until the subject withdraws from the study or dies. A subject that has a Dose Limiting Toxicity (DLT) may be dose reduced or be withdrawn from the study depending upon the decision of the Safety Monitoring Committee (which includes the Sponsor, Medical Monitor and the study investigator) in Part 1.				

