Part	2: BVD-523, recommended Phase	2 dose (RP2D), taken orally with	at least 8 ounces of water twice-daily		

Sponsor:	Investigational Product:	Developmental Phase:
BioMed Valley Discoveries, Inc.	BVD-523	Phase 1/2

for each 21 day cycle. Dosing of each subject may continue until the subject is discontinued from the study. A subject that has a Dose Limiting Toxicity (DLT) may be dose reduced or be withdrawn from the study depending upon the decision of the Safety Monitoring Committee (which includes the Sponsor, Medical Monitor and the study investigator).

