## 7.2 DISCONTINUATION OF INDIVIDUAL PATIENTS

Patients are to be withdrawn from the study for any of the following reasons:

- Withdrawal of informed consent
- Disease progression (at the discretion of the PI)
- Unacceptable toxicity
- Changes in the patient's condition which render the patient unacceptable for further treatment in the judgment of the PI
- At least 3 interruptions of BVD-523 intake of > 7 days each, or 8 consecutive days
- Patient becomes pregnant (withdrawal is required)
- Patient is lost to follow-up

Patients will also to be withdrawn at any time if the Investigator concludes that it would be in the patient's best interest for any reason. Protocol violations do not lead to patient withdrawal unless they constitute a significant risk to the patient's safety.

Patients can voluntarily withdraw from the trial for any reason at any time. They are to be considered withdrawn if they state an intention to withdraw, fail to return for visits, became lost to follow up for any reason, or if any of the following occurs:

- Discovery of patient ineligibility
- Significant errors in treatment compliance of at least three interruptions of 7 days each, any treatment interruption of ≥8 consecutive days, or incomplete dosing for greater than 7 days
- Missed / unscheduled / off-schedule / incomplete / incorrect assessments that result in patients being put at risk.

In Part 1 of the study, patients who withdraw at any time due to unrelated AEs preceding the last visit of Cycle 1 (Day 22) will constitute an early discontinuation and must be replaced in order to ensure proper data accrual for dose escalation decisions. A patient who experiences a DLT in Cycle 1 and withdraws before Day 22 either because of the toxicity or otherwise, will nonetheless have that DLT counted in the assessment of potential cohort expansion and/or dose escalation (Table 3.2).

In Part 2 of the study, patients who withdraw at any time preceding the last visit of Cycle 2 (Day 43) will constitute an early discontinuation and will not be replaced and will be evaluated in the Intent to Treat analysis. If patients withdraw due to progressive disease or AEs, replacement of such patients potentially introduces bias into the study. If a patient withdraws for other reasons, replacement of the patient will be decided by the Safety Monitoring Committee.

The investigator must determine the primary reason for a patient's withdrawal from the study and record this information on the eCRF.

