### 10.2.3 Per Protocol

The per-protocol (PP) population for efficacy evaluations will consist of all patients of the mITT population who completed the study without a major protocol deviation.

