#### Table 10.1Per Cycle Study Visit Definitions

Visit Description	Study Day
Visit 1: Screening	Day -28 to -1
Visit 2: Baseline / Drug Dispensing / Initiation of Treatment	Day $1 \pm 0$
Visit 3: Treatment Phase	Day 8 ± 1
Visit 4: Treatment Phase	Day 15 ± 1
Visit 5: Final Visit	Day 22 ± 1

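### Per-protocol membership requires completing an open-ended study, and completion is never defined, so the set is indeterminate and, as written, can select on outcome

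*SAP*

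**What the plan says.** SAP 5.4 builds the PP set from mITT subjects who take at least one dose, who "complete the first protocol-specified tumor measurement evaluation (except for study drug-related AE"), and who "complete the study without a major protocol deviation (see Section 8.6"). It then states that "the PP population will be used for calculating MTDs in Part 1 and response in Part 2". Protocol 10.2.3 is shorter: mITT patients "who completed the study without a major protocol deviation". It has no dose or tumor-assessment condition, so the two definitions differ, but both require completion.

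No treatment length is fixed. In the protocol synopsis (Test Product, Dose and Mode of Administration), the Part 1 text reads "Dosing of each subject will continue until the subject withdraws from the study or dies" and the Part 2 text reads "Dosing of each subject may continue until the subject is discontinued from the study". SAP 3.1 runs 21-day cycles until progression, toxicity or another withdrawal criterion. Protocol 7.2 opens its list with "Patients are to be withdrawn from the study for any of the following reasons", and the list includes progression (at the investigator's discretion) and unacceptable toxicity.

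SAP 8.1 reports subjects who completed separately from those who withdrew prematurely. Its premature reasons include death, progression, unacceptable toxicity and a residual category. SAP 14.2 lists four Part 2 response tables: AML and MDS, each on mITT and on PP.

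**The concern.** A membership rule should let two programmers working independently build the same set. This one does not, because the term that decides membership has no definition and the design supplies no obvious one. A patient who progresses or stops for toxicity has withdrawn, and a patient in lasting remission is still being treated.

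Two things are at stake. In Part 2, a completion rule that turns on progression, toxicity or death makes membership depend on the outcome being summarized, so a PP response rate could differ from the mITT rate through selection alone. In Part 1, SAP 5.4 names the same set for the MTD, where the informative patients include those who stop early because of toxicity.

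**Working it through.** **The plan's own figure.** Protocol 10.1.2 gives 20 subjects per group, a true response rate of 10%, and an 88% chance of at least one response. Per group, 1 − 0.9^20 = 0.878, which reproduces it. For both groups jointly, 0.878² = 0.772, which does not. The 88% is therefore a per-group figure at n = 20. It does not mention PP, and neither document states an expected PP size.

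**What completion could mean.** The candidate anchors are:

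| Source | What it implies | PP set that follows |
|---|---|---|
| SAP 8.1 | Progression, toxicity, death and other reasons are all premature withdrawal | Nobody, or only subjects still on treatment at closure |
| Protocol 8.2 | The end of the treatment period is Day 22, for medication recording | Everyone reaching Day 22 without a major deviation |
| Protocol Table 10.1 | "Visit 5: Final Visit" is Day 22 ± 1, in a table headed as per cycle | The same, if read as the end of study |
| Protocol 7.2 | A Part 2 withdrawal before Day 43 is an early discontinuation | Everyone reaching Day 43 without a major deviation |
| SAP 13 | Completing is an exit distinct from discontinuing | Not determined |

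None of these is linked to PP. SAP 8.6, to which SAP 5.4 refers, covers deviation categories and their major/minor classification; it does not define completion.

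**Size in Part 2.** Two of the four response tables use PP (14.2.1.1.2 and 14.2.1.2.2): 2/4 = 50%. The strictest reading gives PP n = 0. For the Day 43 reading no retention rate is stated, so I assume 50% to 90% of 20 per group:

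- PP n = 0.5 × 20 = 10 to 0.9 × 20 = 18.
- If leaving is unrelated to response, the chance of at least one response at 10% is 1 − 0.9^10 = 0.651 to 1 − 0.9^18 = 0.850, against 0.878 at n = 20.
- If those who leave are all non-responders, the count of responders stays the same and the rate rises. With 2 responders in 20 (2/20 = 10%), the PP rate would be 2/18 = 11.1% to 2/10 = 20%.

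The second case is the more realistic worry, since early exits for progression are not responders.

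**Part 1.** Protocol 7.2 says that a patient with a Cycle 1 DLT who withdraws before Day 22 still has that DLT counted. SAP 5.4 excuses a missed first assessment when it is due to a drug-related adverse event, but that exception does not extend to the completion condition that follows. The same patient is thus kept by one clause and removed by the next. SAP 12.3 also plans the Part 1 analysis once subjects have been assessed for one full cycle. At that point continuing patients have completed nothing unless completion means Day 22. The SAP display list, whose entries are labelled Part II, puts the table of doses selected as MTD and RP2D (14.3.1.4) on the Safety Population, not on PP.

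**The assessment named in SAP 5.4.** Protocol Table 6.3 and SAP Table 3.1 schedule disease status, bone marrow aspirate/biopsy and cytogenetics, first after baseline at Cycle 1 Day 22. Neither schedules a tumor measurement.

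**The case against.** A reader might infer that the PP set is empty. The documents do not support that as the only reading. Protocol 7.2 treats only a Part 2 withdrawal before Day 43 as an early discontinuation, so a patient leaving later has a document-based claim to count. Protocol 8.2 ends the treatment period at Day 22. SAP 13 separates completing from discontinuing, SAP 8.1 expects some completers, and the schedules have a combined final-visit and early-discontinuation column. Treatment beyond progression is allowed. Table 10.1 is a per-cycle table, so its final visit may simply be the last visit of a cycle and need not contradict Table 6.3. The synopsis sentence about dosing until withdrawal or death is Part 1 text; the Part 2 sentence is looser. All of this stands, and it makes the set indeterminate rather than demonstrably empty.

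A reader might also infer that completion will be judged case by case once responses are known. No text says so. What SAP 8.6 leaves to review is deviations, which are classified before the tables are produced. Nor does the completed row in SAP 8.1 draw on PP: its denominator is mITT, and the disposition table is on the Screened Population.

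Finally, the consequence is limited. The mITT response tables have no completion condition, no formal efficacy analysis is planned, and no Part 2 decision rule depends on PP. That also stands. It bears on severity and does not supply the missing definition.

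**Conclusion.** The point holds. Completion is a stated condition of PP membership, it is undefined, and the anchors in the documents give sets that differ from nobody to nearly everyone who reaches the first post-baseline marrow. On SAP 8.1's categories the rule selects on outcome in two of the four response tables. For the Part 1 MTD, the population in SAP 5.4 conflicts with Protocol 7.2 and does not match the Safety Population used for Table 14.3.1.4; these must be reconciled.

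The size cannot be fixed from the documents. The 10 to 18 per group, and the rates that follow, rest on my assumed 50% to 90% retention to Day 43. The 11.1% to 20% illustration further assumes 2 responders, both retained. The mITT response result survives under every reading. This should be corrected before Part 2 outputs are produced, but it does not threaten the main Part 2 summary.

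**What to change.** - **SAP 5.4:** delete the completion condition and keep the requirement of no major deviation. Replace the tumor assessment with the scheduled Cycle 1 Day 22 disease-status/bone marrow assessment.
- **MTD population:** reconcile SAP 5.4 with Protocol 7.2 and with Table 14.3.1.4, so that one population is named and its treatment of patients who withdraw with a DLT is explicit.
- **SAP 8.1:** tie the completed category to one observable event, or drop it and report reasons for ending treatment.
- **Protocol 10.2.3:** align at the next amendment.

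The cost is SAP wording now, with no new data. Protocol 10.4 requires sponsor, IRB/EC and health authority approval for any protocol change, so the small protocol edit is better carried with the next amendment than made on its own.

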#### 2.3 STUDY ENDPOINTS

## 2.3.1 Primary Endpoint

The primary safety endpoints are the DLTs and MTD for BVD-523 administered alone in subjects with AML or MDS (Part 1) and the MTD for BVD-523 administered at the RP2D dose in subjects with AML or MDS with or without RAS mutant positive disease (Part 2).

As this is a Phase 1/2 study, there is no formal primary efficacy endpoint; however, clinical response will be assessed.

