#### 9.1 PRIMARY ENDPOINT ANALYSIS

As this is a Phase 1/2 study, there is no formal primary efficacy endpoint.

The primary safety endpoints are the DLTs and MTD for BVD-523 administered alone in subjects with AML or MDS (Part 1) and preliminary efficacy (AML/MDS response) of BVD-523 administered at the RP2D dose in subjects with AML or MDS with or without RAS mutant positive disease (Part 2). The MTD and RP2D will be determined based upon the observed DLTs at each dose level as described in the protocol.

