#### 10 SAFETY

Safety analyses will be performed using the Safety Population. Safety will be assessed by examining all adverse events reported during the study including the incidence, and relationship to BVD-523. In addition, safety evaluations will be conducted at Baseline, Days 1, 8, 15, 22, 29, 36, 43, and, in subjects who continue treatment, every 3 weeks or if clinically indicated thereafter. These evaluations will include a targeted ECG where clinically warranted, and clinical laboratory analytes (hematology, chemistry, urinalysis and pregnancy test). An ophthalmologic assessment will also be conducted at baseline, at the end of study and at other visits by an ophthalmologist if clinically indicated.

\*Added as a response option in Note to File dated 21JUL2015

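### SAP 5.4 calculates the Part 1 MTD in the per-protocol population, SAP 5.2 and 10 assign safety analyses to the Safety population, and nothing says which governs

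*SAP*

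**What the plan says.** SAP 5.4 defines the PP population and ends: "Additionally, the PP population will be used for calculating MTDs in Part 1 and response in Part 2". To be in PP, a dosed mITT patient must "complete the first protocol-specified tumor measurement evaluation (except for study drug-related AE") and "complete the study without a major protocol deviation (see Section 8.6"). SAP 8.6 has deviations graded major or minor before the Part 1 outputs are produced, and gives no criteria for major.

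Other parts of the SAP point elsewhere:

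- SAP 2.3.1 classes the MTD as safety: "The primary safety endpoints are the DLTs and MTD for BVD-523 administered alone in subjects with AML or MDS (Part 1").
- SAP 5.2: "The Safety population will be used for all safety analyses". That population is everyone who took at least one dose.
- SAP 10: "Safety analyses will be performed using the Safety Population". The DLT and MTD definitions are then given in SAP 10.2.
- SAP 9.1: "The MTD and RP2D will be determined based upon the observed DLTs at each dose level as described in the protocol".

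Protocol 3.1.4.1 and the MTD paragraph of SAP 3.1 set the criterion: the highest dose cohort with fewer than 33% of patients having a related DLT in the first 21 days.

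**The concern.** One primary endpoint has two analysis sets, and the SAP gives no order of precedence. PP is built around response assessment and study conduct, whereas the MTD depends on toxicity in Cycle 1. A patient who was dosed and had a DLT has supplied the information that the MTD needs, whatever happened later.

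PP can remove that patient in two ways:

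- **A major deviation.** This is the main route. The exception in SAP 5.4 for drug-related AEs is attached to the evaluation requirement and does not reach the deviation requirement.
- **Missing the first disease evaluation** for a reason other than a drug-related AE. A patient who leaves because of the DLT is protected by the exception; one who has a DLT and leaves for another reason is not.

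Cohorts hold three to six patients, so one exclusion can change whether a dose meets the MTD criterion. SAP 12.3 plans a Part 1 analysis to support the discussion of MTD and RP2D, so the choice of set could reach that discussion as well as the report.

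**Working it through.** **Plan figures.** Part 1 has no statistical sample-size calculation (Protocol 10.1.2). The only stated design probability is the 88% for Part 2, which reproduces as 1 − 0.9^20 = 0.878 but has no bearing here. The relevant inputs are the under-33% criterion and the 3+3 cohort rule (three patients, expanded to six after one DLT in three).

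**Smallest change that reverses a cohort's result**

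- All DLTs counted, 2/6 = 33.3%: criterion not met. One DLT patient excluded, 1/5 = 20.0%: met. A single exclusion falling at random on the six hits a DLT patient 2 times in 6.
- All DLTs counted, 1/6 = 16.7%: met. One or two DLT-free patients excluded, 1/5 = 20.0% or 1/4 = 25.0%: still met. Three must be lost to reach 1/3 = 33.3%, not met.

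**How often, under stated assumptions.** The documents give neither an exclusion rate nor a true DLT rate. I assume that every patient, with or without a DLT, leaves PP independently with probability q, and that the true DLT rate is p. The model covers one cohort, without replacement of patients, and is not the distribution of the finally selected MTD.

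Given an observed 2/6, PP meets the criterion if one DLT patient and at least three of the four others remain, or if no DLT patient and at least one other remains:

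P = 2q(1−q) × [(1−q)^4 + 4q(1−q)^3] + q² × (1 − q^4)

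- q = 5%: 0.095 × 0.986 + 0.0025 = 0.096
- q = 10%: 0.18 × 0.948 + 0.010 = 0.181

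On the full count, P(criterion met) = (1−p)^3 + 3p(1−p)^2 × (1−p)^3, and P(cohort ends at 2/6) = [3p(1−p)^2]². Summing over all cohort outcomes:

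| p | Met, full count | Ends 2/6 | q | Not met → met | Met → not met | Disagree |
|---|---|---|---|---|---|---|
| 20% | 0.709 | 0.147 | 5% | 0.0146 | 0.0003 | 0.0149 |
| 20% | | | 10% | 0.0283 | 0.0020 | 0.0303 |
| 30% | 0.494 | 0.194 | 5% | 0.0197 | 0.0002 | 0.0199 |
| 30% | | | 10% | 0.0385 | 0.0015 | 0.0400 |
| 40% | 0.309 | 0.187 | 5% | 0.0194 | 0.0001 | 0.0195 |
| 40% | | | 10% | 0.0389 | 0.0009 | 0.0398 |

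At q = 25% disagreement would be 8% to 10%, and at 50% it would be 18% to 20%. I give the last figure little weight: over half of its met-to-not-met part comes from treating an empty PP set as not meeting the criterion.

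**The case against.** The strongest reply is that SAP 5.4 is the specific instruction and SAP 5.2 and 10 are general ones, so a programmer could simply apply 5.4. SAP 9.1 names no population, and it sits in a section whose default sets are mITT and PP. That default is for efficacy analyses, however, and 9.1 itself calls the MTD a safety endpoint and refers to the protocol's rule. Reading the specific over the general is possible, but the SAP does not adopt it.

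Several passages might be taken as further contradictions; they are better treated as support:

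- Protocol 7.2 counts a Cycle 1 DLT in a patient who withdraws before Day 22, but for cohort expansion and escalation. It does not mention a reported MTD or deviations.
- Protocol 10.2.3 describes PP for efficacy, without forbidding other uses.
- The table of selected MTD and RP2D doses in SAP 14.3.1 uses the Safety population, but it is a Part II display.

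A reader might also infer that requiring study completion empties PP, since treatment runs until progression. That is a strained reading: it would equally empty the Part 2 response analysis.

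The probabilities are fairly called illustrative. Equal loss ignores the drug-related AE exception, which protects some DLT patients.

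**Conclusion.** The inconsistency is real and should be fixed. As written, SAP 5.4 can turn a cohort that fails the MTD criterion (2/6) into one that meets it (1/5). With an assumed equal loss of 5% to 10%, PP and the full count disagree in about 1.5% to 4% of cohorts for true DLT rates of 20% to 40%; given 2/6, PP meets the criterion in 10% to 18%.

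Two stronger inferences are not supported:

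- **That escalation or the RP2D rested on PP.** Protocol 3.1.2 and 3.3 base escalation on Cycle 1 review. SAP 5.2 already refers to the chosen dose ("specifically at the RP2D dose of 600 mg"), and SAP 15 says that this version updates the Part 2 shells. The Part 1 shells are not here, so whether any Part 1 output used PP cannot be checked.
- **That PP demonstrably inflates the MTD.** At 5% to 10% loss nearly all switches are towards meeting the criterion, because 2/6 needs one exclusion and 1/6 needs three. But that loss rate is assumed, and nothing in the documents shows that DLT patients are lost preferentially.

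Exposure is therefore limited to the reported Part 1 MTD and the SAP 12.3 analysis.

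**What to change.** 1. In SAP 5.4, delete the reference to Part 1 MTDs.
2. In SAP 5.2, 9.1 and 10.2, name one set for the Part 1 DLT and MTD summaries: dosed patients who had a Cycle 1 DLT or were evaluable for toxicity through Cycle 1. No observed Cycle 1 DLT is then dropped. The Safety population alone does not quite match, because patients replaced for unrelated AEs stay in it. State how DLT-free patients who leave Cycle 1 early for other reasons are handled, since Protocol 3.1.4.2 and the Part 1 rule in 7.2 provide for replacement only after unrelated AEs.
3. State which set produced any Part 1 MTD already reported.

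Separately, reconcile the MTD wording. The design paragraph of SAP 3.1 refers to fewer than 6 subjects, its escalation table to 6 or fewer, its MTD paragraph and Protocol 3.1.4.1 to under 33%, and SAP 10.2 to at most 1 of 6, citing Section 3.1 for words not found there. Read literally, 1/6 fails the first of these and meets the under-33% and 1-of-6 wordings; no wording makes 2/6 the MTD. Which rule applies is for the sponsor and investigators to settle.

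Cost: SAP wording, one analysis-set flag and a check of any reported Part 1 MTD. No new data or patients are needed.
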